I agree to supervise all testing of the device involving human subjects. I confirm I will ensure Informed Consent requirements will be met for all subjects. I confirm I will ensure Informed Consent of each subject is obtained before any study procedures; protect the rights, safety, and welfare of all study subjects; prepare and maintain accurate, current, and complete records (including Adverse Events); provide timely reports to the IRB; ensure changes are not implemented without prospective IRB approval unless required to eliminate an immediate hazard to subjects; retain records as set out in the protocol; disclose relevant financial information.

Principal Investigator (PI): [name]
PI Printed Name

PI Signature

Date (DD-MMM-YYYY)

CONFIDENTIALITY STATEMENT

This document is the confidential information of Zynex. It is provided to you as an investigator or consultant for review by you, your personnel, and the applicable Institutional Review Board/Ethics Committee. Your acceptance of this document constitutes an agreement that you cannot disclose the information contained herein to others without the prior written consent of Zynex.

PROTOCOL AMENDMENT HISTORY

Version Number	IRB Approval Date	Description of Change(s)
1.0	12-JAN-2021	Initial protocol; no changes
1.1	13-MAY-2021	Increased the number of subjects from 100 to 200 and removed laparoscopic so that both open and laparoscopic procedures are allowed to be enrolled.

[This space is intentionally left blank]

CONFIDENTIALITY STATEMENT

This document is the confidential information of Zynex. It is provided to you as an investigator or consultant for review by you, your personnel, and the applicable Institutional Review Board/Ethics Committee. Your acceptance of this document constitutes an agreement that you cannot disclose the information contained herein to others without the prior written consent of Zynex.

CLINICAL PROTOCOL

SPONSOR: ZMS
PROTOCOL: ZMS-1500-2001
[REDACTED]

[REDACTED] **CONFIDENTIAL**

Page 5 of 33

Table of Contents

1 ABBREVIATIONS AND DEFINITIONS OF TERMS	10
Table 1: Abbreviations and Definition of Terms	10
2 INTRODUCTION	11
3 INVESTIGATIONAL PLAN	11
3.1 OBJECTIVE	11
3.2 STUDY DURATION	11
3.3 STUDY DESIGN	11
4 CM-1500 (“DEVICE”)	11
4.1 DEVICE DESCRIPTION	11
4.1.1 DEVICE DESIGN AND COMPONENTS	12
4.2 PRINCIPLES OF OPERATION	12
4.3 INDICATIONS FOR USE	12
4.4 INTENDED USE	12
5 SUBJECT POPULATION AND SELECTION	13
5.1 POPULATION AND ANTICIPATED NUMBER OF SUBJECTS	13

1 ABBREVIATIONS AND DEFINITIONS OF TERMS

Table 1: Abbreviations and Definition of Terms

Abbreviation	Definition
AE	Adverse event
BPM	Beats per minute
C	Celsius
CFR	U.S. Code of Federal Regulations
CM-1500	Cardiac Monitor, Model 1500
CRF	Case report form
EC	Ethics Committee
ECG / EKG	Electrocardiogram
e.g.	Exempli Gratia (for example)
eCRF	Electronic Case Report Form
FDA	U.S. Food and Drug Administration
GCP	Good Clinical Practice
HIPAA	Health Insurance Portability and Accountability Act
HR	Heart rate
ICF	Informed Consent Form
ICH	International Council for Harmonisation
IFU	Instructions for Use
IRB	Institutional Review Board
ISF	Investigator Site File
ISO	International Organization for Standardization
lb.	Pound; unit of mass
ohms	Unit of electrical resistance, plural
OTC	Over-the-counter
mL	Milliliter
MRI	Magnetic Resonance Imaging
PACU	Post-anesthesia Care Unit
PHI	Protected Health Information
PI	Principal Investigator
PPG	Photoplethysmogram
SAE	Serious adverse event
SOP	Standard Operating Procedure
Sub-I	Sub-Investigator
UADE	Unanticipated Adverse Device Event
ZMS	Zynex Monitoring Solutions

2 INTRODUCTION

Postoperative hemorrhage incidence can vary depending on the type of surgery, but it can lead to severe clinical complications ranging from mild anemia to fatal hemorrhagic shock. One study conducted by Mañas-Gómez et al. (2011) evaluated 107 post-pancreaticoduodenectomy (PD) patients between January 2005 and December 2008 and found that 16.82% (18/107) patients hemorrhaged after PD. Of those, four (4) of the eighteen (18) patients hemorrhaged early (< 24 hours).¹ The study also found that hemorrhage after pancreatic resection may be considered a complication with a high mortality rate. Ansari et al. (2016) conducted a retrospective observational study on 500 consecutive patients undergoing major pancreatic resections.² The study found that 13.6% (68 patients) developed post-pancreatectomy hemorrhage.²

Monitoring and detecting these fluid changes postoperatively can be complicated, and standard operating procedures vary. The Cardiac Monitor, Model 1500 (CM-1500), uses a personalized approach by non-invasively and simultaneously monitoring five (5) physiological parameters, including bioelectrical impedance, ECG Amplitude, PPG Amplitude, heart rate, and skin temperature. [REDACTED]

[REDACTED] When the monitoring session starts, each patient starts with a Relative Index of 100 signifying parameters near their original baseline value. The Relative Index value acts as a combinational score [REDACTED]

[REDACTED]

[REDACTED]

3 INVESTIGATIONAL PLAN

3.1 OBJECTIVE

The primary objective is to evaluate the changes in the Relative Index in post abdominal or pelvic surgery patients (both laparoscopic and open procedures).

3.2 STUDY DURATION

Enrollment is expected to take up to 12 months. Data analysis is expected to take up to 6 months after enrollment is completed.

3.3 STUDY DESIGN

The study is a prospective, single-arm, non-randomized, non-controlled, single-center study enrolling adult subjects.

4 CM-1500 (“DEVICE”)

4.1 DEVICE DESCRIPTION

The CM-1500 is a U.S. Food and Drug Administration (FDA) cleared non-invasive monitoring device that simultaneously monitors five (5) parameters of a patient's body.

Parameters include bioelectrical impedance, heart rate, ECG amplitude, PPG amplitude, and skin temperature. A combination of these parameters is represented by a single number known as the Relative Index value. [REDACTED]

[REDACTED] The Relative Index is a unique functionality of the Zynex CM-1500.

4.1.1 DEVICE DESIGN AND COMPONENTS

The CM-1500 is an all-inclusive device that includes the following components: display monitor (1), power supply (1), trunk cable (1), wrist cuff with attached PPG finger glove (1), wrist strap (1), and electrode array set (2). The wrist cuff with attached PPG finger glove may be cleaned and reused. The wrist strap is single-subject use. The electrode array sets are single-use, single-subject.

4.2 PRINCIPLES OF OPERATION

The CM-1500 measures bioelectrical impedance (ohms), heart rate (BPM), ECG amplitude, PPG amplitude, and skin temperature (°C). As parameters change, towards indications of fluid change/imbalance, the Relative Index, [REDACTED]

[REDACTED], will compound these changes into a singular value [REDACTED]

When the monitoring session starts, every patient will start with a Relative Index of 100, signifying the combination of physiological parameters is near or at their original baseline values for all five monitored parameters. All parameters are continuously measured and tracked during a monitoring session. ECG and PPG amplitude values are only visible on the Advanced monitoring session display mode, as selected in the Setup screen.

4.3 INDICATIONS FOR USE

Per the device's FDA clearance, the indications for use including monitoring of the following parameters and their relative changes, indicative of relative changes in fluid volume in adult patients: bioelectrical impedance, heart rate, ECG amplitude, and PPG amplitude.

4.4 INTENDED USE

Per the device's FDA clearance, the CM-1500 is intended to be used in professional medical environments, i.e., hospitals, clinics, and research institutions. The CM-1500 is a standalone device intended for desktop use, where device operation is to be performed as uninterrupted patient monitoring. The CM-1500 shall only be used by a qualified device operator. The operator shall have knowledge of the system and data interpretation obtained via medical education, system documentation, and specific courses. The device does not report any diagnosis but provides numerical values; it is ultimately the

physician's responsibility to make proper diagnosis and judgments based on these values.

5 SUBJECT POPULATION AND SELECTION

5.1 POPULATION AND ANTICIPATED NUMBER OF SUBJECTS

We anticipate up to 200 adult subjects who meet the inclusion and exclusion criteria to enroll in the study.

5.2 SUBJECT INCLUSION CRITERIA

- I.1 Ability to provide written informed consent
- I.2 Ability and willingness to comply with study procedures and duration requirements
- I.3 18 years of age or older
- I.4 Undergoing an abdominal or pelvic surgery within the next 10 days, be it laparoscopic or open procedure

5.3 SUBJECT EXCLUSION CRITERIA

- E.1 Females who are pregnant or breastfeeding
- E.2 Participation in other clinical studies involving experimental drugs or devices
- E.3 Undergone an amputation of the left upper extremity
- E.4 Diagnosed with Dextrocardia
- E.5 Subjects who have a Pacemaker

5.4 SUBJECT SCREEN FAIL CRITERIA

Subjects who are determined to be a Screen Fail may be replaced.

- SF.1 After Enrollment, the subject is found not to meet the inclusion/exclusion criteria. Enrollment is defined as the subject has provided verbal Informed Consent.

5.5 SUBJECT WITHDRAW / EARLY TERMINATION CRITERIA

Subjects who are withdrawn from the study before using the device may be replaced. Subject withdrawal/early termination criteria are listed below.

- W.1 The subject requests to be withdrawn from the study or withdraws consent.
- W.2 The subject refuses to comply with the required study procedures.
- W.3 An Adverse Event (AE) (related to the investigation or not) makes the continuation of the subject impossible or inadvisable.
- W.4 The Investigator determines it is in the subject's best interest to discontinue from the study.
- W.5 The Sponsor terminates the Investigator, Site, or the Study.

5.6 CONCOMITANT MEDICATIONS/ CONCURRENT MEDICATIONS

All concomitant medications will be recorded from screening through study completion.

[figure not shown]
5.6.1 PROHIBITED MEDICATIONS

Prohibited medications include any experimental drugs while participating in the study (E.2).

6 STUDY GROUPS & ASSIGNMENT

This study is a prospective, non-randomized, non-controlled study. Each subject will undergo the same procedures.

7 STUDY PROCEDURES

7.1 ENROLLMENT

A subject has enrolled in the study after the subject has provided written informed consent.

7.1.1 INFORMED CONSENT/ RESEARCH INFORMATION SHEET

All potentially eligible subjects will undergo formal screening by members of the research teams at each site and confirmed by the site Investigator to be a candidate for the study. The PI or his designee will review and explain the contents of the informed consent document to the eligible subject. The potential subject or family member will be informed of the purpose of the study, the randomization procedure, and the risks and benefits of participation. The potential subject will also be informed that he/she may refuse to participate, and that even if he/she consents to participate he/she may withdraw from the study at any time.

If the subject does not consent to participate, he/she will not be admitted to the study.

7.1.2 SCREENING

Screening procedures are estimated to take approximately 1 hour. Screening procedures include obtaining demographics, medical and surgical history, and concomitant

medications. This information is gathered via chart review and may be self-reported by the subject.

7.1.3 DEMOGRAPHICS

Demographic information, including the subject's year of birth or age, sex, gender, race, and ethnicity, will be recorded at Screening.

7.1.4 MEDICAL & SURGICAL HISTORY

Relevant medical and surgical history will be recorded at the Screening. This includes any medical condition(s) diagnosed or surgeries that occurred before Screening through study completion. The height (inches), weight (pounds), and the type of surgery the subject is undergoing will also be recorded.

7.1.5 CONCOMITANT MEDICATIONS

Concomitant Medications (conmeds) are defined as prescription, over-the-counter OTC drugs, or dietary supplements a subject takes while participating in the study and 2 weeks prior. All concomitant medications will be recorded at Screening through study completion.

7.2 VISIT 1

Visit 1 is estimated to take approximately 2-6 hours. Visit 1 includes preparing the device for use, preparing the subject for device use, operating the device (monitoring session), and observation. Visit 1 will occur on the same day as Screening.

7.2.1 PREPARING DEVICE FOR USE

The Investigator or qualified designated study personnel will prepare the device for use by referencing the Instructions for Use (IFU) manual and following the study-specific steps outlined below.

- S1. Complete the Unpacking, Inspection, and Accountability procedures and associated forms (refer to IFU for the full procedure).
- S2. Ensure the device is in a secure and stable location (refer to IFU for the full procedure).
- S3. To supply power to the CM-1500, connect the power supply cord to the display monitor and an electrical outlet. The light will illuminate on the power adapter when it is connected to power.
- S4. To connect the display monitor to the wrist cuff, connect the CM-1500 wrist cuff trunk cable to the display monitor. The cable should double-click into the correct insertion position.

- S5. Connect the CM-1500 wrist cuff to the trunk cable. The cable should double-click into the correct insertion position.
- S6. Power on the device by pressing the external “ON/OFF” button located on the right side of the display monitor.
- S7. Press the “SETUP” button and select the desired user preferences, patient information, device storage mode, and device information. Press “SAVE” after all desired setup options are selected.
 - a. On the “SETUP” screen, complete user preferences, subject information (sex and subject number), data storage mode, and review device information. By pressing “SAVE,” the device will return to the Monitoring Screen.
- S8. Insert a USB external storage drive (refer to “Data Storage Mode” in the IFU). The USB external storage drive should be labeled externally with the subject number. The USB should display a solid red light.

7.2.2 PREPARING THE SUBJECT FOR DEVICE USE

After the device is prepared for use, the Investigator or qualified designated study personnel will prepare the subject for device use by referencing the Instructions for Use (IFU) manual and following the study-specific steps outlined below. The subject’s position (supine, prone, fowlers, R/L lateral recumbent) throughout the study may be recorded. The subject will be prepared for device use within 15 minutes (but no longer than 1 hour) after the subject’s surgery. Monitoring/device use will occur in the recovery room and PACU.

- S9. Clean the subject’s skin on his or her left wrist.
- S10. Take the small white connector/electrode array and remove the transparent plastic film attached to the electrodes to expose the adhesive. Place the small white connector/electrode array on the dorsal (top) of the subject’s left wrist. The white connector shall be pointed medially (inward) towards the subject’s body.
- S11. Take the large blue connector/electrode array and remove the transparent plastic film attached to the electrode to expose the adhesive. Place the large blue connector/electrode array on the left side of the neck’s base and down across the front of the shoulder (above the clavicle). The blue connector shall point away from the neck, extending toward the direction of the left shoulder.
- S12. Place the wrist cuff on the subject’s left wrist (above or over the top of the white electrode array), with the trunk cable connection point up the arm, and secure the wrist strap around the left wrist. The cuff should be snug with no gap between the

wrist cuff and skin. The wrist cuff should not slide or rotate without being too tight or restricting blood flow.

- S13. Place the PPG finger glove on the subject's left digitus II manus (Index) fingertip. The white cable/top side of the finger glove should be on the dorsal (top) side of the finger. The fingertip shall be touching the end of the inside of the glove. Fingernails will often protrude from the end of the finger glove, which is normal.
- S14. Examine the trunk cable to ensure that it is connected securely to the CM-1500 display monitor and the wrist cuff.
- S15. Connect both CM-1500 electrode array sets to the corresponding electrode lead cables protruding from the wrist cuff. The blue connector/electrode array set shall connect to the blue lead cable connector on the wrist cuff. The white connector/electrode array shall connect to the white lead cable connector on the wrist cuff. The lead cable connectors are shaped to match the electrode connectors.

NOTE: Ensure connectors are properly aligned before inserting (DO NOT FORCE THE CONNECTION).

7.2.3 DEVICE USE/OPERATION

The Investigator or qualified designated study personnel will operate the device by referencing the Instructions for Use (IFU) manual and following the study-specific steps outlined below. Device operation will begin within 15 minutes (but no longer than 1 hour) after the subject's surgery. Sites will not use the device for clinical decisions but instead follow their standard operating procedures for monitoring postoperative subjects.

- S16. Start the monitoring session by pressing "START" on the CM-1500 display monitor/monitoring screen. A message will appear informing the user that the monitoring session is in progress. The device will begin to measure all five (5) parameters.
- S17. As monitoring continues, the display will show ECG and PPG pulse waveforms along with the Relative Index graph over time. [REDACTED]

[REDACTED] The subject should remain in a supine position (with an allowance to be 30 degrees head up) if possible.

- S18. Continue the monitoring session for at least 60 minutes but no longer than 6 hours postoperatively. The device will monitor until "STOP" is pressed on the monitoring screen. Document any observations or adverse events that occur during the monitoring session.

S19. After the monitoring session is stopped, remove the electrode array sets from the subject and dispose of the electrodes per site guidelines.

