7.2.4 OBSERVATION

The site will follow its standard operating procedure (SOP) to monitor postoperative subjects in the recovery room and PACU. The Investigator or qualified designated study personnel will continue monitoring the subject and observe the subject for at least 1 hour but no longer than 6 hours postoperatively. Any observations can be recorded (by using the mark event button on the CM-1500 device), but it is not required as all relevant events will be recorded in the patients medical records as per the SOP of the site. Observations may include but are not limited to indoor temperature of the postoperative recovery room or PACU, time and type of medication delivery, vital sign data (as obtained as part of the sites SOP), and the subject's position. Following/using the site's SOP, should the subject show signs of hemorrhage or a potentially poor outcome, the site will note this in the EMRs including time and date of the observation.

After the observation period is complete, the monitoring session will be stopped, and the electrode array sets will be removed and disposed of. Redacted medical records will be provided to the Sponsor.

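### In the readable text, the live Relative Index graph is not masked from the personnel who observe subjects and document events, so the outcome record used in section 12.4 may not be independent of the index

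*Combined protocol and SAP*

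**What the plan says.** Section numbers follow the body of the protocol, not its table of contents.

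- **Display.** Section 7.2.3, step S17: "As monitoring continues, the display will show ECG and PPG pulse waveforms along with the Relative Index graph over time". Redacted blocks follow this sentence directly.
- **Place.** Section 7.2.2: "Monitoring/device use will occur in the recovery room and PACU".
- **Operator.** Section 7.2.3: "The Investigator or qualified designated study personnel will operate the device by referencing the Instructions for Use (IFU) manual". Step S18, one of the operating steps, also asks for observations and adverse events during the session to be documented.
- **Observer.** Section 7.2.4 gives the same role the watching: "The Investigator or qualified designated study personnel will continue monitoring the subject and observe the subject for at least 1 hour".
- **Recording of bleeding.** Under routine site procedures, section 7.2.4 provides: "should the subject show signs of hemorrhage or a potentially poor outcome, the site will note this in the EMRs including time and date".
- **Event marking.** Section 7.2.4: "Any observations can be recorded (by using the mark event button on the CM-1500 device), but it is not required".
- **Safeguard.** Section 7.2.3: "Sites will not use the device for clinical decisions but instead follow their standard operating procedures for monitoring postoperative subjects". Section 10.1 repeats that no clinical decisions will rest on the device's information.
- **Use of the record.** Section 12.4 groups results by subject outcome, hemorrhagic complications in particular, and evaluates how well the CM-1500 indicates that the complication is present or absent.

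The readable text has no instruction to cover or hide the index, no separation of the operator from the person recording events, and no assessor masked to the index.

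**The concern.** A performance evaluation needs an outcome that is established without knowledge of the index under test. Here the index is on a screen at the bedside while the outcome is being established. Someone who sees the Relative Index change may check the subject sooner or make a fuller entry. Someone who sees a steady trace may do less. Neither act has to be a clinical decision based on the device, so neither clearly breaches the rule in sections 7.2.3 and 10.1.

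Having a masked person classify outcomes afterwards would not fully repair this, because that person would read a record the index may already have shaped. Section 3.3 describes a single-arm study without controls, so no comparison group could reveal the effect. Section 10.1 calls the study pivotal, which raises the importance of a clean reference record.

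**Working it through.** **Step 1. The plan's own figures.** There is no power or precision figure to reproduce: section 12.1 gives up to 200 subjects on grounds of feasibility. The hemorrhage percentages cited in section 2 do reproduce: 18/107 = 16.82% and 68/500 = 13.6%.

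**Step 2. Roles and rule side by side.**

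| Function | Who | Sees the index? |
|---|---|---|
| Operates device (7.2.3) | Investigator or study personnel | Yes |
| Documents events in session (S18) | Same role, as an operating step | Yes |
| Observes subject (7.2.4) | Same role | Yes, unless told otherwise in redacted text |
| Notes hemorrhage signs in EMR (7.2.4) | The site | Not stated; possible, given the location |
| Treats the subject | Site staff under SOP | Not stated; possible, given the location |

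The rule on clinical decisions bears on the last row. The middle rows, which generate the outcome record, are not covered by it.

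**Step 3. How many events might there be?** Input: 4 early bleeds (under 24 hours) among 107 patients in the pancreaticoduodenectomy series cited in section 2. Assumption: that rate applies to 200 subjects.

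- Rate: 4/107 = 3.74%.
- Expected events: 200 × 4/107 = 7.48, about 7.
- Exact (Clopper-Pearson) 95% limits: lower = Beta quantile 0.025 with parameters 4 and 104 = 1.03%; upper = Beta quantile 0.975 with parameters 5 and 103 = 9.30%.
- In 200 subjects: 200 × 0.0103 = 2.1 and 200 × 0.0930 = 18.6, about 2 to 19.

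This study takes any abdominal or pelvic surgery and monitors for at most 6 hours, so fewer events are plausible.

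**Step 4. What could one or two records do?** Section 12.4 sets no cut-off for the index and does not name sensitivity, so sensitivity stands in here for whatever measure is chosen. Assume 7 true bleeds, 4 of them flagged by the index: 4/7 = 57%.

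- One unflagged bleed goes unrecorded: 4/6 = 67%. Two: 4/5 = 80%.
- Care prompted by the index averts one flagged bleed, which then counts as a false positive: 3/6 = 50%.

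A sign recorded only because the index was seen adds one to both numerator and denominator. With 7 recorded events including that one, k of them flagged, the shift is k/7 − (k−1)/6 = (7−k)/42. That is 6/42 = 14 points for k = 1, 3/42 = 7 points for k = 4, and 0 for k = 7. With 2 recorded events the shift is k/2 − (k−1) = (2−k)/2, that is 50 points for k = 1 and 0 for k = 2.

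These figures show leverage. They do not estimate the bias, because nothing in the documents says how often anyone reacts to the screen.

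**The case against.** **The redaction may hide a display instruction.** Redacted blocks come directly after the S17 sentence, and operation also relies on an IFU that is not included. This stands as a limit on confidence: the point is confined to the readable text. Section 4.2 mentions a setup choice for showing ECG and PPG amplitude values, but no readable text describes hiding the index.

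**The plan already has a safeguard.** The rule on clinical decisions appears twice, and section 7.2.4 ties monitoring and hemorrhage notes to the site's SOP. A reader might infer that nothing protects care. The documents do not support that. For care, what remains is unverified compliance. For detection and recording, the rule does not apply.

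**Treating staff are not shown to be watching.** A reader might infer that those who treat bleeding view the graph. The documents name only the Investigator or study personnel as operators and observers, and the site as recorder. Overlap with treating staff is plausible from the location but is not stated.

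**The direction is unknown.** A reader might infer that agreement with the index must be inflated. Step 4 shows it can fall as well: treatment prompted by the index could avert a recordable bleed.

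**The primary objective is descriptive.** Section 3.1 asks only about changes in the index. That is correct, and it limits the reach of the point to the performance evaluation in section 12.4.

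**Conclusion.** The concern holds for the readable text. The index is visible to the role that observes subjects and documents events, care staff may also see it, and section 12.4 evaluates the device against the resulting record. The rule on clinical decisions reduces the effect on care but does not make detection and recording independent of the index.

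The size and direction of any bias cannot be derived from the documents. It matters because events are likely to be few: about 7 in 200, with limits of about 2 to 19, on the assumption that 4/107 carries over, and plausibly fewer.

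A reader might take 7 as a ceiling, or 14 and 50 points as the usual effect of one record. Neither is supported. Seven is a point estimate from 4 events, and the 14- and 50-point shifts are the largest values of the step 4 formulas, reached only at k = 1.

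The plan should be amended. This is not grounds to call the study invalid.

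**What to change.** Amend steps S16 to S18 and section 7.2.4 as follows.

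1. Once signal quality is confirmed after START, keep the CM-1500 display covered or turned away from the care team until STOP. Only the operator views it, for lead and signal checks, and does not relay Relative Index values.
2. Take hemorrhage signs for section 12.4 from the site's SOP record in the EMR. Reword S18 and the mark-event option to match, so that operator entries made in view of the index do not supply that outcome. Adverse event documentation continues as the protocol requires.
3. Record on the CRF whether care staff saw the index.
4. In section 12.4, report results with and without those cases as a descriptive sensitivity check. State that seeing the index may depend on the index itself, so the exclusion can select on it, and that with few events it may remove much of the information.

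If redacted text already shields the display, only items 2 to 4 are needed.

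**Cost.** A short amendment and one CRF item. An operator is already required, and step S8 already has a USB drive inserted for data storage. The operator must lift the cover to check leads. Where the operator is also the person noting events, another member of the existing care team makes the EMR hemorrhage entry; the site should confirm that this is workable. The change puts into practice what sections 7.2.3 and 10.1 already intend and leaves care under the site's SOP.
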